### Questionnaires

At each time point (baseline, post, follow-up 1, follow-up 2), internalizing symptoms will be assessed using multiple informants (adolescent and parent). Additionally, adolescents will self-report on their self-injurious thoughts and behaviors, trait rumination, and trait mindfulness. Finally, parent-reported demographics will be obtained at baseline, and adolescent satisfaction with the application will be obtained at post. Questionnaires will take adolescents approximately 30 minutes to complete and less than 10 minutes for parents. Questionnaires will be completed online using Qualtrics (a survey software platform with secure data storage) except for the demographics form which will be completed on paper to avoid storing any identifying data on the server.

*Internalizing symptoms.* Depression will be assessed using the gold-standard, self-report Children's Depression Inventory (CDI; Kovacs, 1992). This 27-item questionnaire assesses behavioral, cognitive, and physical symptoms of depression and has high reliability and validity ( $\alpha=.88$ ). Anxiety will be assessed using the Multidimensional Anxiety Scale for Children (MASC; March, Parker, Sullivan, Stallings, & Connors, 1997), a 39-item reliable and valid index of anxiety in youth ( $\alpha=.88$ ). It yields a total score along with subscales for physical symptoms of anxiety, harm avoidance, social anxiety, and separation anxiety. Parent-reported internalizing symptoms will be assessed using the 5-item, internalizing subscale from the Pediatric Symptom Checklist (PSC; Jellinek & Murphy, 1988), a widely-used 35-item measure of psychopathology in youth with sound psychometric properties. All of these questionnaires have shown change in response to interventions in previous research.

*Self-injury.* Thoughts and behaviors related to suicide and NSSI will be assessed with the self-report form of the Self-injurious Thoughts and Behavior Interview (SITBI; Nock, Homberg, Photos, & Michel, 2007), a highly reliable and valid assessment tool used with adolescents.

*Rumination.* Trait rumination will be assessed with the rumination subscale from the CRSQ (Abela, Brozina, & Haigh, 2002). This 13-item subscale has demonstrated good reliability and validity ( $\alpha=.88$ ).

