### **Assessment of Safety**

Questionnaires assessing self-injury (including suicidal thoughts and behaviors) will be collected from adolescents at four time points (baseline, post-intervention, and three follow-up periods). Participants who indicate suicidal ideation (by responding to an item on the Children's Depression Inventory indicating that they want to kill themselves, i.e., scoring a 3 on item 9) or serious self-injurious behavior (by responding affirmatively to questions on the Self-injurious Thoughts and Behaviors inventory indicating having a suicide plan or attempt in the past year/week/since the last assessment) will be contacted by the PI, a licensed clinical psychologist with extensive experience doing research and treatment for self-injury. The PI will assess risk by talking with the participant and determine whether contact with a mental health professional is warranted. If necessary, the PI will talk with the adolescent's parent to determine whether the participant is currently in treatment, and if so, will advise the parent and adolescent to make contact with their mental health professional. If a participant requests confidentiality regarding serious self-injurious behavior, we will remind them that this is one of the exceptions to confidentiality because we are seriously concerned for their safety. Every effort will be made to allow the adolescent some control in how the information is presented to the parent (i.e., the adolescent tells the parent or the PI tells the parent), but serious concerns will be communicated with parents, regardless, for safety. For participants not currently under the care of a mental health professional, we will provide a list of local mental health resources and help the family with the referral. We will re-contact families to monitor the participants and determine whether contact with a mental health professional has been made. For participants deemed in imminent risk of suicide, we will inform the parent and advise them to transport the subject to an emergency room or call 911 for assistance with transportation.

Participants will report on their daily mood during the active intervention period (three weeks) and during the optional follow up periods (6 months). In order to monitor and address any potential distress or dissatisfaction during the active intervention period, we will invite participants to contact us with concerns. During our twice-weekly emails to motivate

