participants, we will tell them that they should contact us if they are having any difficulties or feeling upset so that we can talk with them by phone and intervene as needed (e.g., conduct a suicide safety assessment as described above).

In all cases, we will document conversations and interactions with subjects and any health professionals they ask us to contact on their behalf. We will also report any adverse events or unanticipated problems to the appropriate party (e.g., IRB). Because of the low risk involved in the proposed study, the PI will be responsible for carrying out this data and safety monitoring plan.

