### **Adverse Event**

We do not anticipate any risks, as no serious adverse events have been reported in the literature with respect to brief mindfulness interventions. Potential serious adverse events would include hospitalization and suicide attempt. To protect participants against foreseeable risks, participants who indicate serious suicidal concerns will be excluded from or withdrawn from the study until these concerns are resolved. Potential adverse events may include increases in suicidal thoughts or behaviors, breach of confidentiality, upsetting experiences, distress or dissatisfaction as the result of assessment or use of the app. We will ask both participants and their parents about any adverse events that may have occurred during the active intervention period (e.g., upsetting experiences, distress or dissatisfaction as the result of assessment or use of the app). Adverse and serious adverse events will be reported to the appropriate individuals (see section below).

Written informed consent and assent will be obtained by trained research assistants (RAs) during the laboratory visit to Lawrence University at the beginning of the study. The RA will bring the parent and adolescent into a private room and read the assent form to the adolescent. The RA will ask the parent and adolescent separately if they have any questions about the study and answer them. If the parent signs the written consent form, then the RA will say to the adolescent, "Would you like to be in the study and complete the activities? If you say yes, this means you have read this paper or had it read to you and want to be in the study. If you say no, that means you do not want to be in the study. You can say yes or no. Being in the study is your choice. No one will be mad or upset if you do not say yes, sign this paper, or even change your mind later." If the adolescent indicates a definite "yes", the RA will obtain their signature and certify the assent procedure was followed.

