To protect against a potential breach of confidentiality, the EMA data are stored on a secure, password protected website, without any identifying information. The questionnaire data are also stored on a secure, password protected website, without any identifying information. Data collected during the first lab visit are obtained in separate, private rooms for each parent and child. Family background and contact information (i.e., identifying information) will be collected on paper and stored in a locked file cabinet in a locked room only accessible to study staff. No information collected from the adolescent participants will be shared with parents unless there are serious concerns about the child's safety (i.e., suicide concerns or child abuse). Participants and project staff will communicate via phone, email, and text regarding scheduling and completing study materials, but no data or sensitive information will be shared.

The trial will be stopped should findings suggest that the intervention is resulting in mean suicide and/or self-injury levels to increase to a level of clinical concern (e.g., ideation with a plan, attempts, or completions).

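### The only trial-level stopping rule is tied to a mean suicide/self-injury level, although the harms it names are individual events and no by-arm count during the trial is planned

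*Combined protocol and SAP*

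**What the plan says.** The rule closes the Adverse Event section of the combined protocol and SAP. It begins "The trial will be stopped should findings suggest that the intervention is resulting in" and continues "mean suicide and/or self-injury levels to increase to a level of clinical concern (e.g., ideation with a plan, attempts, or completions". The section does not define the level, and it gives no comparator for the increase, no threshold and no review schedule.

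The surrounding safety provisions act on individuals:

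- **Assessment of Safety.** An adolescent who scores 3 on the suicidal item of the Children's Depression Inventory, or who reports "having a suicide plan or attempt in the past year/week/since the last assessment", "will be contacted by the PI, a licensed clinical psychologist". The PI assesses risk and involves parents and professionals as needed. Adverse events go to the IRB or other appropriate party, and "the PI will be responsible for carrying out this data and safety monitoring plan".
- **Adverse Event.** Suicide attempt and hospitalisation are named as potential serious adverse events. Further, "participants who indicate serious suicidal concerns will be excluded from or withdrawn from the study until these concerns are resolved". Participants and parents are asked about "any adverse events that may have occurred during the active intervention period".
- **Questionnaires.** Adolescents report self-injurious thoughts and behaviours themselves: "At each time point (baseline, post, follow-up 1, follow-up 2".
- **Statistical Analysis Plan.** Self-injury appears as one of four outcomes of the indirect-effect model. There is no safety table and no by-arm look while the trial is running.

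**The concern.** The quantity in the rule does not match the harms that the rule names. A plan, an attempt or a death happens to one person, and is expected in few participants if in any. The rule asks the PI to judge whether an average has risen because of the intervention, but gives no count by arm and no trigger.

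The participants are 12 to 15 years old and are selected for rumination, which the Background calls an important risk factor for self-injury and suicidal ideation. If a cluster of attempts arose in one arm, the PI would know each case but would have no agreed basis for deciding whether the stopping condition was met. Two careful people could reach opposite answers from the same data.

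**Working it through.** The plan gives no stopping threshold, safety event rate or power figure, so there is no figure to reproduce. The Sample section gives 150 participants at 1:1, so 150 / 2 = 75 per arm.

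**Step 1. Can the named events enter a mean?**

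| Event | Source | Enters a questionnaire mean? |
|---|---|---|
| Death | Named in the rule | No. There is no later self-report |
| Attempt or plan, participant stays in | Self-injury questionnaire at each time point | Yes |
| Attempt or plan, participant withdrawn | Adverse Event section | Uncertain. The text does not say whether questionnaires continue |

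What an event does to the mean depends on the undefined level. If the level is the proportion with an event, the mean loses nothing beyond the first and third rows. If it is a graded score, improvement in milder ideation could offset new attempts.

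**Step 2. Is attribution possible?** The rule applies only if the intervention is the cause. One case cannot show that; it needs the arms compared. From Assessment of Safety through the Statistical Analysis Plan, no such comparison is scheduled during the trial.

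**Step 3. How would a count trigger behave?** All event risks here are assumptions, because the documents give none. Let X and Y be the numbers of participants with an event in the intervention and control arms over the 15 weeks, each binomial with n = 75. The expected count is 75 × 0.02 = 1.5 at 2%, 75 × 0.04 = 3 at 4% and 75 × 0.06 = 4.5 at 6%.

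- One look at 15 weeks: P(X − Y ≥ k) = Σ over i − j ≥ k of P(X = i) × P(Y = j).
- Three looks, after 3, 9 and 15 weeks: each arm's 15-week risk p is split 3/15, 6/15 and 6/15, that is 20%, 40% and 40%. For a participant still event-free, the risks in the three periods are 0.2p, 0.4p / (1 − 0.2p) and 0.4p / (1 − 0.6p). The cumulative counts are carried forward exactly, and the trigger fires at the first look with X − Y ≥ k.
- After every event: 200,000 simulated trials per row. This is an upper bound for any schedule of looks.

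| Risk, intervention v control | One look, excess ≥ 3 | Three looks, excess ≥ 3 | Every event, excess ≥ 3 | Three looks, excess ≥ 4 |
|---|---|---|---|---|
| 1% v 1% | 0.021 | 0.023 | 0.025 | 0.004 |
| 2% v 2% | 0.068 | 0.076 | 0.090 | 0.023 |
| 3% v 3% | 0.111 | 0.129 | 0.159 | 0.051 |
| 4% v 2% | 0.304 | 0.326 | 0.364 | 0.172 |
| 6% v 2% | 0.573 | 0.597 | 0.638 | 0.418 |

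The first three rows are false triggers and the last two are detections. The three-look figures treat participants as passing each look together. Individual lab visits and weekly enrolment monitoring suggest staggered entry, so real use lies between the three-look and every-event columns.

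**The case against.** The strongest reply is that the rule is loosely worded but workable. It speaks of what findings suggest, which leaves room for judgement, and it names plans, attempts and completions as the level of concern. Only the research assistants are described as masked. The PI holds the key linking IDs to names, contacts every flagged case and runs the monitoring plan, so with few events the PI could count them by arm. In a small trial described as low risk, with IRB reporting, judgement may be enough. A numeric trigger also has limits: it is weak, it cannot see harm common to both arms, and it could be read as permission to wait.

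Much of this stands. The PI is not unaware of cases, and individual protection is sound. The limits of an excess trigger are real, so it should not be used alone. What remains is that the written rule names the wrong quantity, and nothing in the supplied text commits anyone to the by-arm comparison that the rule implies. The Adverse Event section points to a later section on who receives reports. That section is not in the supplied text, so the point is limited to what is visible.

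Three stronger readings are tempting, and the documents do not support them:

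- A reader might infer that attempts would be masked by improvement elsewhere. That needs a graded composite, and none is described.
- A reader might infer that unequal recall windows prevent the rule from firing. That needs a comparison with baseline, which the rule does not specify. The documents also do not assign windows to visits, and between randomised arms the windows are the same.
- A reader might infer that stopping waits for a significant difference between arms. No test or p-value is planned for stopping.

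**Conclusion.** The point holds as a mismatch between the stopping rule and the harms it names, together with the lack of a planned by-arm look. It should be corrected, but it does not show that participants are unprotected.

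Two parts need no assumption: a death cannot enter a self-report mean, and attribution to the intervention needs a comparison of arms. Two parts are conditional: the loss of withdrawn participants depends on whether their questionnaires stop, and offsetting depends on how the level is scored.

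The size of the replacement's benefit rests on assumed 15-week risks. An excess of 3 or more gives about 2% to 13% false triggers at three looks, and up to about 16% with continuous checking. It catches a doubling from 2% in about a third of trials and a tripling in about 60%. An excess of 4 or more lowers the false triggers to about 0.4% to 5% at three looks, and the detections to 17% and 42%. Neither threshold can establish safety.

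**What to change.** In the stopping paragraph of the Adverse Event section:

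1. Replace the mean with the cumulative number of participants with a new post-baseline suicide plan, attempt or death. Count each participant once, by randomised arm. Include withdrawn participants and events known only from adverse-event reports. Update the count as each assessment or report arrives.
2. State that any attempt or death goes to prompt PI and IRB review whatever the arm balance, so that harm common to both arms is not missed.
3. Have the investigator and IRB set in advance the between-arm excess that pauses enrolment and app use for review. The table gives 3 or 4 as examples.
4. State that the excess is a trigger for review and not a test of safety, and that the PI may still stop earlier on judgement.
5. Extend the adverse-event question, now limited to the active intervention period, to both follow-ups by adding it to the online questionnaires for participants and parents. The self-injury questionnaire already given at those visits supplies plans and attempts.

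Keep the individual procedures as they are.

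The cost is a wording change, IRB notification, one short by-arm table from data largely already collected, and one added question at two visits. The downside is that someone other than the masked research assistants sees event counts by arm during the trial.

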### **Statistical Analysis Plan**

**General Analytic Strategies.** The number of participants recruited and retained will be documented, and comparisons will be made on all study variables between those who complete and those who drop out of the study in order to inform external validity. Compliance and intervention dose will be assessed with time-stamped electronic records generated through the app. All data will be inspected for normality and transformations will

be applied as needed. Missing questionnaire data will be handled using multiple imputation if data are missing completely at random (Enders, 2013).

**Specific Aim 1.** There are multiple ways to assess participants' engagement to determine the acceptability of the intervention. The first two involve examining how much adolescents use the mobile application. We will examine compliance during the 3-week intervention period by comparing the amount of application use (as recorded electronically) in the intervention group to the control group. We will also examine use during the follow-up periods (12 weeks), when it is optional. Both of these usage questions can be answered with t-tests comparing use between groups.

The other two ways of measuring acceptability are more direct. Participants will complete a satisfaction questionnaire during the post-assessment, and we will compare scores on these questions between groups using t-tests. Finally, participants in the intervention condition will answer a question after each mindfulness exercise regarding how helpful it was using a 0-100 scale ranging from not at all helpful to extremely helpful. Scores on this question can be averaged and examined separately for each type of mindfulness exercise to see if they fall above the benchmark of 50, indicating that adolescents find them helpful in the moment. With all statistical analyses, we will use best current practices regarding correction for multiple tests.

**Specific Aim 2.** Testing of the hypothesis that the intervention will reduce symptoms through the mediating effect of reduced rumination will be accomplished by capitalizing on both trait-level questionnaire data and state-level EMA data. Using trait-level data, an indirect effect model will be tested to examine the effect of condition (EMA-only vs. EMA + Mindfulness) on each outcome (depressive symptoms, anxiety symptoms, parent-reported internalizing symptoms, and self-injury) through the indirect effect of rumination (see Figure 2). These analyses will be accomplished using the PROCESS macro (Hayes, 2013) for SPSS (IBM Corp.) which relies on bootstrapping to generate bias corrected confidence intervals. This approach is particularly well-suited for testing mediation models with relatively small sample sizes. It also allows for the addition of covariates and/or moderators if inclusion of them are warranted. For example, if there are sex differences in rumination and/or symptoms, as is likely based on previous research (e.g., Hilt, McLaughlin, & Nolen-Hoeksema, 2010), sex can be covaried or tested as a moderator of effects (**Exploratory Aim**) using methods described by Preacher, Rucker, and Hayes (2007). Dose can also be examined as a covariate, to test whether variability in use of the mobile application affects outcomes. These indirect effects models will be tested at each time period (post, follow-up 1, and follow-up 2). If the hypothesis is supported for

[figure not shown]

Figure 2. Conceptual indirect effect model. Note that moderators (e.g., sex) may also be included.

the post-intervention time period, it will be helpful to see if effects are maintained at 6 and 12 weeks. If the hypothesis is not supported at the post-intervention period, it will be possible to examine delayed effects at the follow-up time points. For example, the intervention could reduce rumination first and have a delayed effect on symptoms.

The primary hypothesis can also be examined on a finer-grain time scale using state-level EMA data to test whether a mindfulness exercise results in reduced negative mood immediately or at subsequent time points relative to each person's average level of mood. Relatedly, we can examine whether mindfulness exercises reduce state rumination compared to one's average level of state rumination and if so, test mediation. Similar to the trait-level models, covariates (i.e., between-person factors such as sex, SES, and race/ethnicity) may be included if warranted. These multilevel models will be estimated in Mplus (Muthén & Muthén, 1998-2015) using maximum likelihood estimation with robust standard errors to account for the nested nature of the data. This approach will allow for the examination of between- and within-person variation in outcomes and is consistent with current recommendations for handling missing data (Baraldi & Enders, 2010).

Although rumination is the proposed mediator, we can also test an alternative mechanism, i.e., changes in mindfulness (**Exploratory Aim**). Another mindfulness intervention found that changes in state mindfulness predicted changes in trait mindfulness (Kiken, Garland, Bluth, Palsson, & Gaylord, 2015). Furthermore, there appears to be an inverse relationship between trait mindfulness and depressive symptoms (e.g., Way, Creswell, Eisenberger, & Liberman, 2010). Thus, it is possible that the intervention will improve symptoms by increasing mindfulness, reducing rumination, or both. Both trait- and state-level mindfulness can be included as mediators in the above-mentioned models (Preacher & Hayes, 2008).

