### **Sample**

We will recruit 150 adolescent girls and boys, ages 12-15. This age range was chosen to capture the developmental period directly preceding increased rates of depression (Hankin et al., 1998), providing an opportune window for prevention. Participants will be recruited through a recruitment letter mailed to students enrolled in grades 7-10 at a large, local, public school district with over 5000 students in our target age range. In order to maximize the potential of targeting the proposed mechanism, we will only enroll adolescents who report at least moderate baseline levels of trait rumination. This will be accomplished through a 2-question phone screen. Once parents verbally consent and the child has verbally assented, we will ask them to respond to two questions from the Children's Response Style Questionnaire (CRSQ; Abela, Brozina, & Haigh, 2002) that assess brooding, a particularly maladaptive aspect of rumination (Treynor, Gozalez, & Nolen-Hoeksema, 2003). The aggregate of these two questions are highly correlated with the full rumination subscale from the CRSQ ( $r = .79$ ,  $p < .01$ ) and have been associated with depressive symptoms and NSSI in previous work by the PI (Hilt et al., 2008). Adolescents who meet the screening criteria (age 12-15, score of 2 or higher on the brooding questions, and physically and cognitively able to use a mobile application) will be invited to participate in the study. Once they provide written consent and assent, they will be randomly assigned to a condition: EMA only or EMA + Mindfulness at a 1:1 ratio (i.e., ~ 75 participants per condition).

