### **Mindfulness Intervention**

In the EMA + Mindfulness condition, participants have a 67% chance of receiving a mindfulness exercise, unless their sad or anxious mood rating is 90 or above, in which case their chance is 85%. This graded strategy was chosen so that participants would not be able to easily figure out the mood rating that results in an exercise and so that participants would have a greater chance of receiving an exercise when they most needed it.

If an exercise is assigned, participants are prompted to enter how much time they have to engage in an activity (from 0-15 minutes). There are three 1-minute exercises (written instructions for focusing on the breath, sounds, or physical sensations); six 3-5 minute exercises (guided audio focusing on breathing, sounds, or body scan); and five 10-12 minute exercises (guided audio focusing on breath, body scan, or mountain metaphor).

Participants who indicate having less than 5 minutes receive one of the 1-minute exercises, those who indicate having at least 5 minutes receive either a 1-minute or a 3-5 minute exercise, and those who indicate having at least 12 minutes receive any exercise. Exercises are randomly assigned based on these parameters. The guided audio exercises were chosen based on those freely available that represent the type of mindfulness exercises typically found in MBSR courses, appeared accessible for adolescents, featured a variety of voices, and performed well in pilot testing. Following each mindfulness exercise, participants were prompted with the same EMA questions plus an additional question asking how helpful the activity was, rated on a 0-100 sliding scale.

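### Completers and dropouts are to be compared without a stated split by arm and only for external validity, so the plan has no check on whether different kinds of participants leave each arm

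*Combined protocol and SAP*

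**What the plan says.** The SAP, under General Analytic Strategies, makes two statements about retention. First, "The number of participants recruited and retained will be documented". Second, the plan is that "comparisons will be made on all study variables between those who complete and those who drop out of the study in order to inform external"; the stated purpose is thus external validity alone. Neither statement mentions arm.

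Other parts of the plan come near this point without covering it:

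- Missing questionnaire data are to be multiply imputed on condition that they are missing completely at random. The contents of the imputation model are not given.
- The between-group t-tests under Specific Aim 1 concern app use and satisfaction, not dropout.
- The maximum-likelihood approach under Specific Aim 2 belongs to the momentary (EMA) models, not to the questionnaire outcomes.
- The trait-level mediation models under Specific Aim 2 estimate the effect of condition at post, follow-up 1 and follow-up 2. Covariates are optional there, and baseline adjustment is not prespecified.

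**The concern.** Randomisation makes the arms comparable at entry. Whether those still providing data remain comparable depends on who leaves each arm. This is a question of internal validity, and a comparison of all dropouts with all completers is not built to answer it.

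The documents give reasons why leaving could depend on arm. Both arms answer the momentary questions, but "In the EMA + Mindfulness condition, participants have a 67% chance of receiving a mindfulness exercise", with a higher chance at high sad or anxious ratings, and the momentary questions are repeated after each exercise. The Adverse Event section also provides for withdrawal of participants with serious suicidal concerns. Self-injury is an Aim 2 outcome, so if the intervention changes those concerns, withdrawal would depend on both arm and outcome.

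At stake is a report that completers and dropouts did not differ, followed by a condition effect on rumination or symptoms that partly reflects who remained.

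**Working it through.** The documents state no dropout rate, effect size or power, so there is no figure to reproduce. What follows illustrates the mechanism.

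**Input from the documents.** The Sample section says "We will recruit 150 adolescent girls and boys, ages 12-15", allocated 1:1, so 150 / 2 = 75 per arm.

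**Assumed inputs.** Dropout share p = 0.20 in each arm (15 dropouts, 60 completers); baseline SD of 1 within each group; no treatment effect; two-sided 5% tests. Dropouts lie s SD from their arm's baseline mean, with s1 in the mindfulness arm and s2 in the control arm.

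**Formulas.**

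1. The arm mean is zero, so 0 = 0.2 × s + 0.8 × m, and completers sit at m = −0.25 × s.
2. Baseline gap between arms among completers: 0.25 × (s1 − s2) in absolute size.
3. Within an arm, dropouts minus completers: s + 0.25 × s = 1.25 × s.
4. Expected pooled contrast: 1.25 × (s1 + s2) / 2, with SE = √(1/30 + 1/120) = 0.204.
5. Arm-by-dropout interaction: 1.25 × (s1 − s2), with SE = √(2 × (1/15 + 1/60)) = 0.408.
6. Rejection rate: approximately Φ(contrast / SE − 1.96), or the nominal 5% when the contrast is zero.

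| s1, s2 | Baseline gap among completers | Pooled contrast; rejection | Interaction; rejection |
|---|---|---|---|
| +0.5, −0.5 | 0.25 SD | 0; about 5% | 1.25; 1.25/0.408 = 3.06, about 86% |
| +0.5, 0 | 0.125 SD | 0.3125; 0.3125/0.204 = 1.53, about 33% | 0.625; 0.625/0.408 = 1.53, about 33% |
| +0.5, +0.25 | 0.0625 SD | 0.469; 0.469/0.204 = 2.30, about 63% | 0.3125; 0.3125/0.408 = 0.77, about 12% |

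Simulation agrees. In the first row the pooled test rejected in roughly 3% to 6% of runs, depending on how the data were generated, and the interaction test in about 86%.

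**From baseline gap to outcome bias.** With an assumed baseline-outcome correlation of 0.5 to 0.7, an unadjusted completer comparison in the first row is biased by 0.25 × 0.5 = 0.125 SD to 0.25 × 0.7 = 0.175 SD. In the second row the bias is 0.0625 to 0.0875 SD. Adjusting for the baseline value brings the simulated bias to about zero, because dropout in this example depends only on arm and baseline.

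**Range under opposite selection.** Let D be the dropout-minus-completer difference, +D in one arm and −D in the other. The completer gap is then 2pD; the first row has D = 0.625, and 2 × 0.2 × 0.625 = 0.25. For p from 0.1 to 0.3 and D from 0.3 to 0.8, the gap runs from 0.06 to 0.48 SD, the unadjusted outcome bias from 0.03 to 0.34 SD, and the interaction power from about 20% to 99%. The expected pooled contrast is zero throughout.

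**Unequal dropout rates are a separate case.** If condition counts among the study variables compared, 75 per arm gives 87% power to see 10% against 30%, 60% for 15% against 30%, and 40% for 10% against 20%. Such a test compares how many leave each arm, not who leaves.

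**The case against.** The strongest reply is that the bias needs an unadjusted completers-only analysis, which the SAP does not announce. It plans multiple imputation, and a regression-based imputation using arm and baseline removes the bias in the example. That stands as a limit on the size. It does not close the gap, because the SAP specifies neither the imputation model nor baseline adjustment, and makes imputation conditional on an assumption that the pooled comparison is poorly placed to examine.

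Full cancellation needs opposite and balanced selection, and the documents give no reason to expect exactly that. A difference in burden points first to different dropout rates, and exercise length is matched to the time the participant enters, which softens the burden. This also stands: the first row of the table is close to a best case for the criticism.

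The interaction test is no cure. It does no better than the pooled test when only one arm is selective, and worse when both arms select in the same direction.

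A reader might infer more than the documents support:

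- That the 0.25 SD is a spurious treatment effect. It is a baseline gap; the corresponding unadjusted outcome bias is about half to 0.7 of it.
- That the plan commits to a completer analysis, or that the result will be biased. Neither follows from the text.
- That the word for completing is hopelessly unclear. The sentence speaks of leaving the study, and the Procedure section treats later app use as optional. A definition at each wave would help, but this is a minor point.

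**Conclusion.** The concern holds as a gap in the planned checks. No part of the plan examines whether different kinds of participants leave each arm, although this bears on the internal validity of the condition effect in Specific Aim 2. Under the assumed 75 per arm, 20% dropout and opposite 0.5 SD selection, completers differ by 0.25 SD at baseline, and an unadjusted completer analysis is biased by about 0.12 to 0.18 SD at a correlation of 0.5 to 0.7, unseen by the pooled test. If only one arm is selective, the gap is about 0.12 SD and the pooled test detects it about a third of the time. The dropout shares, selection sizes and correlations are assumptions; only the sample size and allocation come from the documents. The change is cheap and worth making.

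**What to change.** Replace the SAP sentence on dropout with text to this effect:

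- At each wave, dropout means that the questionnaire was not submitted, recorded separately from stopping app use.
- Dropout is reported by arm with reasons.
- Baseline variables are shown by arm and dropout status, with the arm-by-dropout interaction, whether or not any test is significant.
- The results are used to judge internal as well as external validity.

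In the trait-level models under Specific Aim 2, prespecify the baseline value of each outcome and of rumination as covariates. Include arm and these baseline values in the imputation model.

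Covariates should not be added only after a dropout difference has been found. Ten baseline variables tested at three waves at the 5% level would give 10 × 3 × 0.05 = 1.5 false positives on average, and adding arm interactions to the outcome models would change the meaning of the condition coefficient in the mediation analysis.

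The cost is SAP wording and a few more descriptive comparisons, with baseline and later questionnaires already being collected. The interaction test has limited power at this sample size, so a null result must not be read as ruling out bias.
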